2.1 Primary Endpoint (Composite)

The **primary endpoint** is implant success through six-months of post-functional loading. The implant success criteria will be collected on a per patient level and are a composite of implant survival, health and efficacy measures, based after criteria of Buser, et. al. ¹, including:

- Presence of the implant at its site of implantation; and,
- Absence of a recurrent peri-implant infection with suppuration; and,
- Absence of mobility, which will be assessed at multiple timepoints. Specifically,
 - Immediate stabilization (implant placement, Visit 3) is assessed by applying a torque of 20 Ncm applied directly to the implant 15 minutes after implantation.
 - Short-term stabilization (implant uncovering, Visit 5) is assessed by applying a torque of 35 Ncm 13 weeks after implant insertion.
 - Continued stabilization is assessed at 6-months post-functional loading (Primary Follow-up, Visit 9) by applying manual palpation.
- Absence of encapsulation determined by a continuous radiolucency around the implant assessed via periapical image.

2.2 Secondary Endpoints

2.2.1 Incidence and Severity of Device Attributed Adverse Effects and Events

The **first secondary endpoint** will be to demonstrate low incidence and severity as well as short duration of adverse device-attributed systemic effects and events as reported by study subjects and/or investigator/monitors throughout the 12-month post-functional loading term.

2.2.2 Long Term Implant Success

The **second secondary endpoint** will be to demonstrate long-term implant success after implants are stabilized with the TN-SM device throughout the 12-month post-functional loading term. The implant success criteria will be collected on a per patient level at each timepoint and are a composite of implant survival, health and efficacy measures, based after criteria of Buser, et. al.¹, including:

- Presence of the implant at its site of implantation; and,
- Absence of a recurrent peri-implant infection with suppuration; and,
- Absence of mobility, which will be assessed by applying manual palpation; and,
- Absence of encapsulation determined by a continuous radiolucency around the implant assessed via periapical image.

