	Restorative Records	6	Health Check, Records for Fabrication of Definitive Restoration (Impressions or scans, shade, jaw relation, etc.), Photographs	3-weeks post implant uncovering			
	Insertion of Definitive Restoration (Baseline)	7	Insertion of Definitive Restoration, Health Check, Satisfaction Survey, Periodontal & Peri-Implant Measurements, Radiographs, Photographs	4 - 6 months post TN-SM device and implant placement			
	3-month Follow-up	8	Health check, Satisfaction Survey, Periodontal & Peri-Implant Measurements, Radiographs, Photographs, Implant Success	3-months post- functional loading			
	6-month Follow-up – Primary Endpoint	9	Health Check, Satisfaction Survey, Periodontal & Peri-Implant Measurements, Radiographs, Photographs, Implant Success	6-months post- functional loading			
	9-month Follow-up	9.5	Health Check, Satisfaction Survey, Periodontal & Peri-Implant Measurements, Radiographs, Photographs, Implant Success	9-months post- functional loading			

Protocol DVAL18041 Version 3.0

	12-Month Follow-up	10	Health check, Satisfaction Survey, Periodontal & Peri-Implant Measurements, Radiographs, Photographs, Implant Success	12-months post- functional loading				
	15-month Follow-up	11	Health Check, Satisfaction Survey, Periodontal & Peri-Implant Measurements, Radiographs, Photographs, Implant Success	15-month post- functional loading				
	18-month Follow-up	12	Health Check, Satisfaction Survey, Periodontal & Peri-Implant Measurements, Radiographs, Photographs, Implant Success	18-month post- functional loading				
	21-month Follow-up	13	Health Check, Satisfaction Survey, Periodontal & Peri-Implant Measurements, Radiographs, Photographs, Implant Success	21-month post- functional loading				
	24-month Follow-up	14	Health Check, Satisfaction Survey, Periodontal & Peri-Implant Measurements, Radiographs, Photographs, Implant Success	24-month post- functional loading				
Study Products:	Commercially a	Tetranite Stabilization Material, TN-SM Commercially available endosseous dental implants Manufacturer's recommended prosthetic components for the implant systems						
Registration Status:	TN-SM is the e	TN-SM is the experimental device under study.						

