3.10 Post-Loading Follow-up Visits

Following crown placement, all subjects will return for routine evaluation of the study site and for evaluation of the TN-SM device function at 3-, 6-, 9-, 12-, 15-, 18-, 21-, and 24-months of post-functional loading. In addition to the routine elements of the site evaluation, the following assessments will be performed: Photographic records will be captured of the study site from lingual (or palatal) and buccal aspects, and the subject will also answer a satisfaction survey (pain, function, and esthetics) at every post-loading follow-up. A standardized periapical image for documentation of crestal bone level and for evaluation of encapsulation of the study will be captured

at 3 months and 6 months post-loading, and every 6 months thereafter (3, 6, 12, 18, and 24 months). A CBCT scan of the region of the study site will be performed at the 3-, 6-, 12-, and 24-month post-loading follow-up visits.

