3.11 Study Assessments

3.11.1 Implant Success

Implant success will be assessed at post-functional loading follow-ups. A successful implant will meet all of the following criteria according to Buser et al.¹; including,

- Presence of the implant at its site of implantation;
- Absence of a recurrent peri-implant infection with suppuration;
- Absence of mobility, which will be assessed at several timepoints. Specifically,
 - Immediate stabilization (implant placement, Visit 3) is assessed by applying a torque of 20 Ncm applied directly to the implant 15 minutes after implantation.
 - Short-term stabilization (implant uncovering, Visit 5) is assessed by applying a torque of 35 Ncm 13 weeks after implant insertion.
 - Long term stabilization is assessed every 3 months post-functional loading until 24months post-functional loading by manual palpation.
- Absence of encapsulation determined by a continuous radiolucency around the implant recorded in a periapical image.

Any dental implant showing excessive bone loss, radiolucency, or infection shall be treated in the manner best suited to the well-being of the subject, including treatment to save the dental implant. Continuous radiolucency, implant loss, recurrent peri-implant infection with suppuration, or implant mobility shall be considered a failure for the purposes of the study.

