3.11.8 Periapical Radiographs

Standardized peri-apical radiographs of the area being treated will be recorded pre-operatively, at surgery after device placement, during implant uncovering, at the prosthetic records visit, at insertion of the definitive restoration, and 3, 6, 12, 18, and 24 months post-functional loading. The radiographs must be of high quality and definition, so as to identify the bone contours in question. Ideally the entire implant should be visible on the radiograph. However, it is not essential that the apical end of the implant is contained within the radiograph; in case it is not, at least three threads from the top of the implant showing first bone-implant contact must be visible in the image. These radiographs will be used for crestal bone level assessment and evaluation of implant success (e.g., presence of encapsulation as determined by a continuous radiolucency around the implant).

Radiographs will be digital, using either a direct sensor system or an indirect system with Photostimulable Phosphor (PSP) plate. The patient-specific, custom stent fabricated during the Qualifying Exam must be used. All settings must be noted and consistently used on subsequent visits. To standardize the series of periapical radiographs, the same customized sensor/phosphor plate holder and beam aiming device will be used throughout the study for each study implant site. The radiographs will be captured with the sensor/phosphor plate placed parallel to the implants and the X-ray beam directed perpendicular to the implants. The digital image should will be saved and the file name will be formatted as follows: Subject number (XX-XX), Subject initials (XXX)_Image date (DD MMM YYYY), i.e., 01- 01_ABC_04 Nov 2019. The files will be uploaded as a DICOM file into the Electronic Data Capture system. The records will contain the kV, mA, and exposure time settings.

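### Does the lack of a scheduled radiograph at 9, 15 and 21 months leave the implant-success endpoint unscorable?

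*Combined protocol and SAP*

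**What the plan says.** Section 2.2.2 defines long-term implant success over 12 months after loading by four components: the implant is present, there is no recurrent suppurating infection, there is no mobility on palpation, and "Absence of encapsulation determined by a continuous radiolucency around the implant assessed via periapical image". It adds that "The implant success criteria will be collected on a per patient level at each timepoint".

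Section 3.11.1 uses the same criteria with the torque tests added, and extends palpation to 24 months. It requires all of them: "A successful implant will meet all of the following criteria". It also sets the failure rule: "Continuous radiolucency, implant loss, recurrent peri-implant infection with suppuration, or implant mobility shall be considered a failure for the purposes of the study".

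On imaging, section 3.10 says a standardized periapical image "for documentation of crestal bone level and for evaluation of encapsulation of the study will be captured" at 3, 6, 12, 18 and 24 months. Section 3.11.8 gives the same post-loading times: "at insertion of the definitive restoration, and 3, 6, 12, 18, and 24 months post-functional loading". The assessment grid agrees, and the visit lists in 5.10, 5.12 and 5.14 include implant success but no radiograph.

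The Synopsis treatment-plan table differs. Apart from one capital letter, every post-loading row carries the same entry: "Health check, Satisfaction Survey, Periodontal & Peri-Implant Measurements, Radiographs, Photographs, Implant Success".

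Sections 7.1 and 7.2 plan descriptive summaries only. Section 7.4.4 rules out imputation.

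**The concern.** Success requires every criterion to be met, one criterion is read from a periapical image, and the criteria are said to be collected at each timepoint. At 9, 15 and 21 months the operational schedule provides neither a periapical image nor a CBCT. Read literally, nobody can confirm the full composite at those visits, and no sentence says how encapsulation is to be scored there. The Synopsis appears to promise a radiograph at exactly those visits.

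A success rate tabulated in those rows could therefore rest on three components while being labelled as four. If the unassessed component were treated as a pass, the rate in those rows could only equal or exceed the true one.

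**Working it through.** **Step 1. Set the visits side by side** (Synopsis treatment plan, assessment grid, sections 3.10, 3.11.8 and 5.8 to 5.15).

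| Month (visit) | Success scored | Synopsis lists radiographs | Periapical in grid and body text | CBCT in grid |
|---|---|---|---|---|
| 3 (8) | yes | yes | yes | yes |
| 6 (9) | yes | yes | yes | yes |
| 9 (9.5) | yes | yes | no | no |
| 12 (10) | yes | yes | yes | yes |
| 15 (11) | yes | yes | no | no |
| 18 (12) | yes | yes | yes | no |
| 21 (13) | yes | yes | no | no |
| 24 (14) | yes | yes | yes | yes |

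The body text's five periapical times are reproduced exactly by the grid. Section 3.11.9 adds a CBCT at 18 months that the grid does not have; this does not touch the three visits in question.

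**Step 2. Count.** Visits with success scored but no radiograph: 8 − 5 = 3. Within the 12-month term of section 2.2.2, the visits are 3, 6, 9 and 12 months, and 4 − 3 = 1 lacks an image. The other two (15 and 21 months) fall after that term. With 20 subjects and no losses, that is 20 × 1 = 20 of 20 × 4 = 80 subject-visits inside the endpoint, and 20 × 3 = 60 of 20 × 8 = 160 over the whole follow-up.

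**Step 3. Check whether a conclusion depends on which version is followed.**

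- Synopsis followed: 8 of 8 visits have an image, 4 of 4 within 12 months.
- Grid and body text followed: 5 of 8, and 3 of 4 within 12 months.
- Under both, the 6-month primary assessment and the 12-month assessment have an image.

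**Step 4. How long could an encapsulated implant go unseen around month 9?** Table 1 allows ± 1 month at 6 months and ± 2 months at 12 months. The gap between the two images is nominally 12 − 6 = 6 months, at least (12 − 2) − (6 + 1) = 3 months and at most (12 + 2) − (6 − 1) = 9 months. A radiolucency that arises in the gap and persists is seen on the 12-month image and is a failure under 3.11.1. It is dated later, but it still counts in the 12-month result.

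**Step 5. Is a composite with components on different schedules foreign to this plan?** No. Section 3.11.1 already assigns one torque test to Visit 3, another to Visit 5, and palpation to every three months after loading. Section 3.10 names the visits at which encapsulation is evaluated. The natural reading is that each component is scored when it is scheduled and that a failure, once recorded, stands.

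**Step 6. How reliable is the Synopsis table on imaging?** It also omits imaging that the grid marks at Visit 1 (full-mouth CBCT or panoramic) and at Visit 6 (periapical, also in 3.11.8 and 5.6). It therefore departs from the grid at five visits, in both directions. One entry repeated down eight rows looks like a generic summary line, not a separate imaging plan.

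**The case for a change.** The strongest case for a change is that correcting the Synopsis does not close the gap. Implant success would still be ticked at three visits without the image its definition requires, and a site could score on three components, leave the item blank or reuse the previous image. The pilot's stated aims include trying out measures and procedures for a larger study, and clarifying the wording costs almost nothing.

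Much of this is true. The plan never writes down how encapsulation is handled at a visit without an image, and the each-timepoint phrase in 2.2.2 is loose. A full-composite success reported at 9 months would not be supported by data from that visit.

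The harmful version, however, needs a rule that scores the missing component as a pass, and no such rule exists. Section 7.4.4 points the other way: encapsulation is simply not assessed at those visits, and carrying an earlier image forward would sit badly with that section. Nor is there evidence that the two centers would image differently; the grid, the prose and the three visit lists agree with each other.

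**Conclusion.** No change to the plan is needed. The contradiction between the Synopsis and the rest of the document is genuine, and those passages should be reconciled whenever the Synopsis is next reissued. It is a clerical matter that does not reach any reported conclusion.

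Its size is one interim visit of four within the 12-month secondary endpoint, plus two visits beyond it. A competent analyst would give presence, infection and mobility at 9, 15 and 21 months, mark encapsulation as not assessed, keep earlier failures as failures, and show the four-component rate at 3, 6, 12, 18 and 24 months. That needs no new data or procedure.

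This rests on three assumptions: the 6- and 12-month images are obtained as scheduled; a continuous radiolucency that appears between images does not clear before the next one; and no reader treats the 9-month row as a conclusion in its own right. The documents do not address the second. A transient radiolucency would escape any schedule of spaced images, and with purely descriptive analysis it would affect only an interim row.

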2.2.3 Crestal Bone Level Maintenance

The **third secondary endpoint** will be to demonstrate crestal bone level maintenance measured directly by two-dimensional periapical radiographic methods showing no more than a 2mm loss of height at the 12-month post-functional loading term.

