component of this study is a composite comprising: (1) First – To demonstrate and evaluate the ability of TN-SM to achieve immediate implant stabilization in sites otherwise unable to provide primary stability without requiring the delay in treatment imposed by the current multi-staged standard-of-care method; (2) Second - To demonstrate and evaluate the ability of TN-SM to achieve short-term stabilization of implants as the device undergoes initial resorption and replacement with new bone; and (3) Third - To demonstrate and evaluate the ability of a TN-SM stabilized implant to achieve implant success (after criteria of Buser, et. al.1) after 6 months of functional-loading while the device undergoes significant resorption, facilitates osteoconduction, and replacement with new bone. In addition to the Primary Endpoints of establishing the Safety and Efficacy of Implant Stabilization and Implant Success throughout the initial 6 months of postfunctional loading, the study also assesses several secondary endpoints over the course of the study and one-year follow-up, as outlined in the sections below. These include assessment of incidence, duration, and severity of adverse effects and events; assessment of implant success; assessment of bone level, volume and density changes; patient satisfaction surveys, and assessment of periodontal and peri-implant health integral to implant success.

There are currently many alternatives for clinicians and patients to choose for use as bone graft materials. While safety and efficacy have been well established for the majority of them, success rates vary both in their ability to allow bone replacement and their ability to maintain volume of bony architecture once placed, and as healing and bone replacement occur over time. Additionally, where bony walls are absent, guided bone regeneration (GBR) procedures are indicated. While also highly successful, these GBR procedures introduce additional risk of treatment failure, post-surgical infection and other complications, as well as increased cost and treatment time for the patient. While not a primary outcome of this proposed study, animal data to date have demonstrated soft tissue exclusion with Tetranite and, therefore, no need for barrier membranes to be used. Additionally, the TN-SM is dimensionally stable as it is replaced by the patient's bone, thereby limiting the need for overfill or secondary grafting procedures.

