3.9 Study Treatment Plan

Subjects enrolled in the study will have had, during the Surgical Visit, a test site which met the criteria of an initially placed implant demonstrating inadequate stability. After implant removal, the TN-SM is applied to the site and the implant is reinserted per the Tetranite IFU – Document # 50001-00 (Appendix 1). Immediate stabilization is assessed by applying a torque of 20 Ncm applied directly to the implant 15 minutes after implantation. This level is a clinically relevant indicator of stability and is expected to be a sub-threshold and nondestructive test.⁴⁸ After successful completion of the torque test, all implants will be closed with a cover screw and soft tissues left to granulate over the socket crests. Monofilament sutures will be used at the discretion of the study site before and after soft tissue adaptation. A standardized periapical image will be captured for documentation of the crestal bone level pre-extraction and after TN-SM device and implant placement.

Two weeks following placement of the TN-SM device and the implant, all subjects will return for evaluation of the study site for healing and possible suture removal. A localized CBCT scan of the region of the study site will be performed and will serve as baseline.

All subjects will return at 13 weeks following the TN-SM device implantation to uncover the implant. At this point, short-term stabilization will be assessed by applying a torque of 35 Ncm to the implant. The test is performed at a clinically relevant torque level to demonstrate readiness for restoration of an implant supported prosthesis.⁴⁹ A healing or standard abutment will be placed during the visit. A standardized periapical image for documentation of crestal bone level and for evaluation of indicators of encapsulation will be captured. Photographic records of the study site will be captured before uncovering surgery and following abutment placement and soft tissue adaptation.

Following a three to four-week healing period, records will be obtained for fabrication of a crown restoration. These records will consist of the following: final impression or scan of the test site dental arch, an impression or scan of the opposing dental arch, a jaw relation record and a shade registration of the dentition. Photographic records will also be captured at this time.

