Contingent upon satisfactory stabilization, the implant will be loaded by the implant crown in appropriate occlusion with an abutment and crown prosthesis no sooner than four months and no later than six months after TN-SM device placement. A baseline standardized periapical image for documentation of crestal bone level and for evaluation of indicators of encapsulation will be captured. Photographic records will be captured of the study site before and after the crown is inserted from lingual (or palatal) and from buccal aspects. If the definitive restoration is inserted provisionally at this time, the provisional insertion date will be treated as the baseline loading date for the purposes of the study and the definitive insertion visit will be recorded as a separate visit.

Any loosened implants that are identified during the course of the study will be considered a failure and will be removed. The remaining Tetranite material will be removed by curetting or drilling the osteotomy until a bleeding bone surface is obtained. The clinician may place a wider or longer implant as appropriate for the tooth position. Otherwise the site will be grafted as per a conventional staged approach.

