6.3.4 ADE Reporting

Adverse device effects must be recorded and submitted to RevBio by completing the AE case report form in the EDC system within five working days of awareness of the event. Safety reporting to the Institutional Review Board (IRB) should occur according to the requirements of the local IRB.

Bone loss reporting: Continuous substantial reduction of the peri-implant bone level is a sign of failure of the implant system. The first European Workshop on Periodontology specified an average marginal bone loss of less than 1.5 mm bone loss within the first year after the insertion of the prosthesis, and thereafter less than 0.2mm annual bone loss as criteria for measuring success.⁵⁰ This has been a standard and a basis for success criteria since it was defined in 1993. A more recent systematic review article in 2012 reported 2 mm of bone loss being universally acceptable

at one year.⁵¹ Based on this information and since this is a pilot study, the central radiologist will flag any bone level changes that are greater than 2 mm in the first year post-functional loading. The study manager will review the flagged values and discuss with the principal investigator whether the bone level change will be reported as an ADE.

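### Does the 2 mm crestal bone limit in section 2.2.3 fail because it names no reference film?

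*Combined protocol and SAP*

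**What the plan says.** Section 2.2.3 defines the third secondary endpoint as crestal bone maintenance on two-dimensional periapical films, "showing no more than a 2mm loss of height at the 12-month post-functional loading term". The synopsis gives the same limit. Both fix the size of the loss and the closing time point (Visit 10); neither names the opening film. Section 7.2 says secondary endpoints are summarized descriptively and gives no change-from rule for this one.

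Section 3.9 describes several films. For surgery: "A standardized periapical image will be captured for documentation of the crestal bone level pre-extraction and after TN-SM device and implant placement". There is another at uncovering. At loading: "A baseline standardized periapical image for documentation of crestal bone level and for evaluation of indicators of encapsulation will be captured". Section 3.11.8 adds a film at the restorative records visit. Section 3.9 also says of the two-week visit: "A localized CBCT scan of the region of the study site will be performed and will serve as baseline".

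Section 6.3.4 uses the same 2 mm figure for safety: "the central radiologist will flag any bone level changes that are greater than 2 mm in the first year post-functional loading".

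**The concern.** A loss needs a start and an end, and 2.2.3 gives only the end. The post-placement film (Visit 3) and the loading film (Visit 7) are both taken to document crestal bone level, and section 3.9 uses the word baseline for two different images. The fourth and fifth secondary endpoints state their time points or reference; the third does not.

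If the choice were open, it could be made after the films are read. It would also decide whether bone lost between placement and loading counts at all. That interval matters for a resorbable device: section 1 describes the second efficacy aim as "short-term stabilization of implants as the device undergoes initial resorption and replacement with new bone". Section 3.1 says the pilot tests measures for a larger study, so an undefined measure could carry over.

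**Working it through.** There is no planned figure to reproduce: the documents give no bone-loss mean or SD, no target proportion and no power calculation for this endpoint. The check has two parts.

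**1. Which film do the documents point to?**

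- Visit 7 is labelled baseline in the synopsis visit list, in both schedule tables and in the heading of section 5.7.
- Section 3.9 says that if the restoration is first inserted provisionally, that date counts as the baseline loading date for study purposes.
- The Visit 7 film is the only periapical film called baseline for crestal bone level. The other baseline in section 3.9 is a CBCT scan; section 2.2.3 restricts the endpoint to periapical films, so it does not compete.
- Section 2.2.5 names definitive restoration as the baseline around the implant for the fifth endpoint.
- The flag in 6.3.4 shares the 2 mm value and covers the first year after loading. One criterion it cites "specified an average marginal bone loss of less than 1.5 mm bone loss within the first year after the insertion of the prosthesis", so that clock also starts at loading.
- Elapsed time agrees. Visit 7 to Visit 10 is 12 months (10 to 14 with the window), close to the one year for which 6.3.4 supports 2 mm. Visit 3 to Visit 10 is 4 + 12 = 16 to 6 + 12 = 18 months (14 to 20 with the window).

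The pre-extraction film shows no implant. On the Visit 3 film, enrolled sites have a gap above 2 mm in at least two directions (5.3.2), and TN-SM may fill it up to the crest (5.3.4). Section 3.11.8 relies on bone-implant contact: when the apex is off the film, "at least three threads from the top of the implant showing first bone-implant contact must be visible in the image". That landmark may be harder to read just after placement than at loading.

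**2. How much could the choice matter?**

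Loss from placement = loss before loading (D0) + loss after loading (D1). A subject with D1 = 1.5 mm passes from Visit 7, and fails from Visit 3 once D0 exceeds 2.0 − 1.5 = 0.5 mm. The 1.5 mm is a ceiling on an average in a cited source, not a subject's expected loss, so this shows only that a reversal is possible.

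For an expected count, assume D0 and D1 are independent and normal with means m0 and m1 and common SD s:

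- from Visit 7: P(D1 > 2) = 1 − Φ((2 − m1)/s)
- from Visit 3: P(D0 + D1 > 2) = 1 − Φ((2 − m0 − m1)/(s√2))

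All three parameters are assumptions: m0 from 0 to 0.75 mm, m1 from 0.5 to 1.0 mm, s from 0.5 to 0.75 mm.

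| Case | m0 | m1 | s | From Visit 7 | From Visit 3 | Difference × 20 |
|---|---|---|---|---|---|---|
| Smallest gap | 0 | 0.5 | 0.5 | 0.001 | 0.017 | 0.3 |
| Middle | 0.5 | 0.75 | 0.5 | 0.006 | 0.144 | 2.8 |
| Largest gap | 0.75 | 1.0 | 0.5 | 0.023 | 0.362 | 6.8 |

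The ends differ by a factor of 6.8/0.3, about 23, and the answer is driven by m0. Section 1 expects TN-SM to be dimensionally stable as bone replaces it. With m0 = 0 the model gives 0.3 to 1.6 subjects, all from added variance. An extreme subject losing 2.5 mm before loading and 0.5 mm after (3.0 mm from Visit 3, 0.5 mm from Visit 7) lies (2.5 − 0.5)/0.5 = 4 SD out before loading in the middle case. Even at m0 = 0.75 and s = 0.75, (2.5 − 0.75)/0.75 = 2.33 SD, a probability of about 1%.

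**The case for a change.** The best counter-argument is that no sentence ties the 2 mm limit to Visit 7. The flag in 6.3.4 is a reporting rule and names no film either. Even if Visit 7 is accepted, loss in the 4 to 6 months before loading enters neither the endpoint nor the flag. At n = 20 each reclassified subject moves the proportion by 1/20 = 5 points: 20/20 has an exact 95% interval of 83.2% to 100%, and 17/20 has 62.1% to 96.8%.

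The first part stands as a point of wording. The second stands only in part. The fourth endpoint follows CBCT bone volume and density from before extraction through post-placement follow-up, though qualitatively and without isolating the interval up to loading. CBCT is also taken at Visit 7. Section 7.2 summarizes dimensional bone changes from periapical and CBCT images without limiting them to the period after loading, and the Visit 3 and Visit 7 films both exist. Table 3 lists bone loss around the implant as an expected device effect, and reporting runs from consent. An added count over 2 mm from Visit 3 would rest on the film that may be hardest to read. The intervals above are not part of the plan, which is descriptive only (7.4), and no required proportion is set.

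Section 7.2 hides subject and time point from the evaluator and does not say who links readings into a change. That is an unwritten operating step. A third party already codes the images, and section 8 refers data-handling detail to a Data Management Plan. It does not show that the flag cannot run.

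**Conclusion.** No change is needed. Section 2.2.3 leaves out its reference film, but the rest of the protocol points to Visit 7, and counting from there matches the period for which the 2 mm figure is supported. This is a gap that analysts fill sensibly, in an untested secondary endpoint of a 20-subject descriptive pilot. A clause naming the film would be tidy, but on this reading it would not alter the result.

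The effect of choosing Visit 3 instead cannot be sized from the documents; 0.3 to 6.8 subjects of 20 reflects assumed means and SDs only. The conclusion rests on the visit labels and section 6.3.4 being read together, and on loss before loading being reported through the CBCT endpoint, the section 7.2 summaries and adverse events.
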